## **Biological Markers**

In Phase I, subjects will donate DNA/RNA/Saliva for genetic and research studies. No clinically validated tests will be performed. The genetics/biomarker component of the protocol will be supervised by [name] (CTVHCS Neuropsychiatry Research Program, Building 205, 3R05 and 3R08) and [name] (CoE Biomarkers and Genetics Core) experts in this area, in collaboration with the PI. See Appendix for Safety Survey. At the BL assessment, participants will be given the option of consenting to all study procedures or all procedures excluding the saliva/blood sample (depending on the phase) and genetic research.

For those who consent to that aspect of the study, participants will donate saliva by spitting into a coded Oragen™ tube at the assessment site. Staff will be trained to avert their eyes when participants are spitting into the test tube to reduce potential embarrassment. The saliva samples will be stored at room temperature in a locked - cabinet present inside a locked office (Building 93, 1A-137) until transported at room temperature by team members to [name] lab in Temple or Waco Building 93 (rooms 2A 116, 2A 117), where the samples will be stored until DNA extraction and testing. Phase I genotyping will be performed at CTVHCS Temple Building 205 and Waco Building 93. According to the work load, the genotyping work will be divided between the two labs (Drs. [name] & [name]).

## **Aims and Hypotheses**

Specific Aim 1. Identify whether a dose-response relationship exists between level of exposure to stressors and subsequent level of functioning.

*Hypothesis 1a.* Greater exposure to pre-deployment stress and trauma will predict lower levels of functioning concurrently and over time.

*Hypothesis 1b.* Greater exposure to deployment-related stress and trauma will predict lower levels of functioning concurrently and over time.

*Hypothesis 1c.* Greater exposure to post-deployment stressors will predict lower levels of functioning concurrently and over time.

Specific Aim 2. Examine whether potentially malleable resilience factors predict higher levels of functioning in returning OEF/OIF Veterans.

*Hypothesis 2a.* Greater use of healthy coping strategies (i.e., acceptance and active coping) will predict higher levels of functioning concurrently and over time.

*Hypothesis 2b.* Greater levels of social support will predict higher levels of functioning concurrently and over time.

*Hypothesis 2c.* Higher levels of neurocognition will predict higher levels of functioning concurrently and over time.

Specific Aim 3. Examine whether psychopathology predicts lower levels of functioning.

*Hypothesis 3a.* Greater PTSD-Depression symptoms will predict lower levels of functioning concurrently and over time.

*Hypothesis 3b.* Greater AUD symptoms will predict lower levels of functioning concurrently and over time.

Specific Aim 4. Test the theoretical model that psychopathology partially mediates the effects of stress, social support, coping, and neurocognition on functioning concurrently and over time.

*Hypothesis 4a.* The hypothesized model (Figure 1) in which PTSD-Depression and AUD symptoms fully mediate the effects of pre-deployment stress, post-deployment stress, and active coping on functioning and partially mediate the effects of neurocognition, deployment stress, acceptance, and social support on functioning will show significantly better fit to the data compared to any of the following alternative models: an independent main effects model, a fully mediated model, or a full partial mediation model.

*Hypothesis 4b.* PTSD-Depression symptoms will fully-mediate the effects of active coping, pre-deployment stress, and post-deployment stress on functioning and will partially-mediate the effects of deployment stress, acceptance, and social support on functioning.

### **Planned Analyses**

The purpose of the longitudinal design is to better understand the functional recovery of returning OEF/OIF/OND Veterans over time and to identify potentially-malleable risk and resilience factors associated with functioning. The study design is based on a measurement model that collects predetermined, repeated assessments every 4 months over a one-year period beginning with a baseline evaluation. Other than these measurement contacts, no experimental manipulations are planned, although participants may participate in treatment programs or be appropriately referred to treatment programs or other research studies during the course of this study. Treatment will be tracked using the *Treatment Involvement Form*, as this may influence course and outcome.

This study will provide a rich dataset from which we will be able to conduct numerous analyses as proposed here, as well as those that are exploratory in nature in order to maximize the impact of the proposed research. Various statistical software programs will be utilized to accomplish the study aims, as appropriate (e.g., SPSS, SAS, mPLUS, AMOS). VA software will be used. Licenses are supported by the VISN 17 CoE as well as local IT (as indicated in original grant budgets). We will also use access software through the secure VA VINCI system (e.g., SPSS). VINCI requires documentation of IRB approval before analyzing data on the VINCI system. With respect to the proposed primary hypotheses, structural equation modeling (SEM; Jöreskog, 1970, 1993) will be the statistical approach employed to examine the relationships among the variables. SEM is essentially a combination of factor analysis and path analysis (Kline, 2005). This type of statistical analysis was chosen to test the hypotheses because it has several advantages over traditional statistical techniques (e.g., multiple regression). For example, SEM corrects for measurement error, which, in turn, improves statistical power. SEM also allows both latent and observed variables to be evaluated within the same model, and it is an especially effective analytical procedure for studying complex relationships among many variables. However, the two most important advantages of SEM over other traditional statistical analyses are: 1) SEM enables users to conduct tests of entire models in a single analysis; and 2) *SEM allows for entire models to be tested against other competing models* (Kline, 2005). Given that the one of the primary aims of the current proposal is to provide a direct test of our hypothesized model of functional outcomes in returning Veterans (Specific Aim 4, Figure 1), SEM appears to be the most appropriate type of statistical analysis to employ as it will enable us to: 1) examine the overall fit of our hypothesized model to the data; and 2) statistically compare our hypothesized model to other competing models (e.g., a main effects only model).

A two-step modeling approach will be used to test each aim (Anderson & Gerbing, 1988; Kline, 2005). First, a confirmatory-factor analysis (CFA) measurement model will be computed to determine the degree to which the underlying latent constructs are statistically accounted for by their corresponding hypothesized observed variables. The hypothesized measurement model that we have proposed (see Table 3) is based on a combination of findings from our pilot data, previous research, and current theory and represents our best estimate of what the measurement model will be. If the hypothesized measurement models are supported by CFA, the structural relationships among the latent variables will be tested in the second step. If the initial hypothesized measurement model is rejected, the suggestions for model respecification offered by Kline (2005, pp 165 - 208) will be followed until an acceptable measurement model is found. Once an acceptable measurement model has been identified, the fit of the hypothesized structural model will be assessed with multiple goodness-of-fit indices, including the Root

Mean Square Error of Approximation (RMSEA), Standardized Root Mean Square Residual (SRMR), Comparative Fit Index (CFI), Normed Fit Index (NFI), and the Akaike Information Criterion (AIC). The hypothesized models will also be compared with other competing models using either the chi-square difference test for hierarchically-related models or the AIC for models that are not nested. Alpha will be set conservatively ( $\alpha = .01$ ) for all analyses in order to minimize the probability of Type I error.

Specific Aims 1, 2, and 3, which hypothesize that stress, coping, neurocognition, and psychopathology will predict functioning in returning Veterans concurrently and over time will be initially tested within the context of an independent main effects model in which each of the hypothesized factors will be simultaneously regressed onto the functioning factor while accounting for the covariances among the predictors. Hypotheses will be considered to be rejected if the regression coefficients are either non-significant (i.e.,  $> .01$ ) or are in the opposite direction of our predictions. To test these hypotheses over time, an identical model will be constructed using level of functioning at 1-year follow-up as the primary outcome variable while co-varying for level of functioning at baseline. In addition, a Cross-Lag Panel design (Ecob, 1987; Farrell, 1994; King et al., 2000; Williams & Peodsakoff, 1989) will be employed to examine the autoregressive associations (i.e., the value of interest is assumed to be a function of the previous values plus a random component) and cross-lag associations between the predictors and functional impairment across time. For example, Figure 3 illustrates the structural aspects of a Cross-Lag Panel design based on two waves of assessments of post-deployment stress and functioning. Within this model, we will test the effects of post-deployment stressors from the prior time period on functioning in the subsequent time period, while accounting for the effects of functioning from the prior time period. Likewise we will test the effects of functioning from the prior time period on post-deployment stressors in the subsequent time period, while accounting for the effects of post-deployment stressors from the prior time period. The Cross-Lag Panel design will enable us to examine the possibility that there may be reciprocal relationships that occur over time involving the predictors of interest and functional impairment. Specific Aim 4, which hypothesizes that psychopathology partially mediates the effects of stress, coping, and neurocognition on level of functioning in returning Veterans concurrently and over time, will be achieved by comparing the hypothesized model with several competing models, which include an independent main effects model, a fully-mediated model, and a complete partial mediation model. The overall fit of the hypothesized model will initially be assessed with multiple goodness-of-fit indices including RMSEA, SRMR, CFI, and NFI. Next, chi-square difference tests and AIC values will be used to compare the hypothesized model against the competing models. It is predicted that the hypothesized model will show good overall fit to the model (e.g., RMSEA  $< .05$ , CFI  $> .95$ ) and that the hypothesized model will fit the data significantly better than the competing models. The regression coefficients for the hypothesized indirect pathways will also be examined for statistical significance (i.e.,  $p < .01$ ). The hypothesized model will also be tested over time. Specifically, level of functioning at year 1 follow-up will be regressed on to PTSD-Depression and AUD symptoms at 8-months, which, in turn, will be regressed on to ongoing stress, social support, acceptance, and active coping at 4 months and deployment stress, pre-deployment stress, and neurocognitive functioning at baseline. By testing the hypothesized model in this manner, we will be able to reduce the possibility that response bias during a particular assessment accounts for the hypothesized mediation results. Testing the model in this manner will also take into account the hypothesized causal ordering (i.e., stress, coping, social support, and neurocognition predict psychopathology, which, in turn, predicts functioning).

Specific Aim 5, which hypothesizes that changes in the use of healthy coping strategies, social support, post-deployment stress, and psychopathology will predict changes in functioning over time, will be achieved by using latent growth curve models (LGMs) to test hypotheses 5a – 5c. LGMs characterize the trends in growth and change functions for individuals over time (Figure 4). This analytic method assumes that individuals change at different rates and that underlying latent variables determine the overall level and shape of individual trajectories (Lawrence & Hancock, 1998; McArdle, 1998). LGMs can be fit using structural equation models, and are capable of describing the behavior or symptom status of individuals in terms of their initial measurement levels and by their trajectories of change from those levels. LGM techniques can also analyze variability in initial levels and trajectories across persons, while providing means to test the contribution of other predictor variables and constructs as determinants of the different levels and trajectories. LGM techniques offer great flexibility for modeling individual growth

trajectories and their effects on outcomes, while accounting for multiple covariates. LGM will be used to examine the degree to which changes in healthy coping, post-deployment stress, social support, and psychopathology predict changes in functioning over time. It is hypothesized that sustained use of healthy coping strategies and social support, or increases in healthy coping or social support, will predict higher levels of functioning over time, whereas sustained high levels of, or increasing levels of, post-deployment stress and psychopathology are hypothesized to predict lower levels of functioning over time.

Specific Aim 6, which proposes to explore whether the proposed risk and resilience factors have differential effects on specific aspects of functioning, will be achieved by testing the hypothesized model (or an alternative model found to provide the best overall fit to the data in relation to global functioning) in relation to each specific aspect of functioning at both baseline and at 1-year follow-up. That is, separate tests of the hypothesized model will be conducted for each specific aspect of functioning (e.g., occupational, family, social, physical). We hypothesize that neurocognition will be most strongly related to occupational functioning, whereas PTSD-Depression and AUD symptoms will be most strongly related to family functioning.

**Power and Sample Size Considerations.** SEM will be used as the analytic strategy for testing all hypotheses. MacCallum, Browne, & Sugawara (1996) describe a method for estimating the required sample size to achieve a given power estimate at specified degrees of freedom ( $df$ ) for both close fitting (i.e.,  $RMSEA = .05$ ) and not close fitting (i.e.,  $RMSEA = .08$ ) models. These  $RMSEA$  values are chosen as points of estimate, since values below .08 are shown to indicate an acceptable but not necessarily close model fit to the data, and values below .05 are shown to indicate an acceptable and close fit to the data (Steiger, 1990; Browne & Cudek, 1993; Hu & Bentler, 1993). The method described by MacCallum and colleagues can also be employed to provide a power estimate for close and not-close fitting models. For the purposes of the current proposal, the software developed by Preacher and Coffman (2006) to calculate power from  $df$ ,  $RMSEA$ ,  $N$ , and alpha using the method described by MacCallum et al. (1996) were used to conduct a power analysis for the proposed study. For SEM equations,  $df$  are equal to the number of observations [i.e., observed variables \* (observed variables + 1) / 2] minus the number of free parameters in the model. Due to the complexity of the proposed models, the  $df$  for our proposed models are high and range from 137 to 922  $df$ , with differences among the models being largely accounted for by differences in model complexity and the number of observed variables included in each model. Power was estimated conservatively by using the model with fewest degrees of freedom to estimate power, as power increases with  $df$  (MacCallum et al., 1996). Setting alpha conservatively at .01, a final sample size of 300 participants (from 400 enrolled) would provide a power estimate of .997 for a close-fitting model with 137  $df$  and .988 for a not-close fitting model with 137  $df$ . In addition, in the event that there is even greater than expected attrition (i.e., attrition rates are greater than 20%), the proposed study would still remain well powered even if as much as 35% of the sample were lost to attrition. For example, leaving alpha set conservatively at .01, a sample size of 195 participants (65% of the original sample size) would still provide a power estimate of .936 for a close-fitting model with 137  $df$  and .822 for a not-close fitting model with 137  $df$ . These results are also consistent with Kline's (2005) rule-of-thumb that sample sizes of 200 or greater are generally well-powered for SEM analyses. Thus, by recruiting an initial sample of 400 participants, we will be well-positioned to retain a sufficiently large sample to remain well-powered throughout the duration of the study, even in the event that attrition rates are higher than expected.

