World Health Organization Disability Assessment Schedule II (WHODAS II)	DV	✓	✓	✓	36 item self-report version assessing functional disability across 7 domains (understanding and communicating, getting around, getting along with people, life activities, work, participation in society, self-care) as well as a total score. The WHODAS-II is becoming widely used in investigations of functional disability with wide-ranging populations and is a primary measure in an ongoing VA/DoD study aimed at developing a measure of functional impairment in active duty service members and Veterans ([name], Pl, Schnurr and Hoge, Co-Investigators).
Inventory of Functional Impairment (IFI)	DV	✓		✓	87 items ([name] et al, 2009). The IFI yields an overall score and 7 subscales: Romantic Relationships with a Spouse or Partner, Family, Work, Friendships and Socializing, Parenting, Education, and Day-to-Day functioning. Higher scores indicate greater functional impairment. Preliminary analyses ( $n = 170$ ) with Veterans show strong psychometric properties, including strong

					internal consistency (Cronbach's alpha ranging from .76 to .91) and construct validity.
Employment Survey (ES)	DV	✓	✓	✓	12 item self-report version adapted from the measure developed by Glynn and colleagues (Mueser, Glynn, and McGurk, 2006) to assess employment status, number of hours worked, income, reasons for not working or working less than full-time, satisfaction with various aspects of current employment, and stability of employment (number of jobs held, reasons for leaving previous jobs) since discharge from active duty military.
Quality of Life Scale (QLS)	DV	✓	✓	✓	16 items (Burkhardt, et al., 1989) assessing how satisfied people are in regards to 16 areas distinct from health status (mate, physical well-being, relationships with others, social, community, and civic activities, personal development and fulfillment, recreation, and independence). Good internal consistency and (alpha .82 to .92) and high test-retest reliability ( $r = .78$ to .84; Burckhardt et al. 2003). Life satisfaction is a central goal of recovery and rehabilitation, and diminished quality of life may influence suicidality and other key outcomes.

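### The Phase I over-time test of Aim 4 omits earlier levels of functioning and symptoms, so stable, correlated scales can give a significant indirect path with no lagged effect

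*Combined protocol and SAP*

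**What the plan says.** All of this is in the combined protocol and SAP, Completed Phases, Phase I.

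- **Outcome equation (Planned Analyses, Specific Aim 4).** The plan states that "level of functioning at year 1 follow-up will be regressed on to PTSD-Depression and AUD symptoms at 8-months".
- **Mediator equation.** The symptoms are the next response, "which, in turn, will be regressed on to ongoing stress, social support, acceptance, and active coping at 4 months", together with deployment stress, pre-deployment stress and neurocognition at baseline.
- **Direct paths.** Under Hypothesis 4a the symptom factors "partially mediate the effects of neurocognition, deployment stress, acceptance, and social support on functioning", so some predictors keep a direct path.
- **Test.** "The regression coefficients for the hypothesized indirect pathways will also be examined for statistical significance", at p < .01. The general rule is "Alpha will be set conservatively", at .01 for all analyses.
- **Reason for the lagged layout.** The authors expect that "we will be able to reduce the possibility that response bias during a particular assessment accounts for the hypothesized mediation results", and that the layout respects the hypothesised causal order.
- **Contrast.** The over-time test of Aims 1 to 3 is specified "using level of functioning at 1-year follow-up as the primary outcome variable while co-varying for level of functioning at baseline". The cross-lag panel described with it also conditions on the preceding period.

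**The concern.** The over-time model is written out term by term, and no earlier functioning or earlier PTSD-Depression or AUD symptoms appear in it. The competing models (main effects, fully mediated, complete partial mediation) are not described as containing them either, so comparing fit is no safeguard.

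Spacing the measurements four months apart deals with bias specific to one assessment. It does not deal with stable differences between Veterans. A Veteran who is persistently low on acceptance, high on symptoms and poor in functioning contributes to both paths at any spacing, whether or not one scale later changes another. The over-time part of the mediation claim would then be read as evidence of sequence when it may only repeat the cross-sectional association.

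**Working it through.** **1. The plan's own figures.** The only Phase I power figures concern overall model fit (RMSEA), with noncentrality (N-1) x df x RMSEA². At N=300, df=137 and alpha .01, the stated .997 (close) and .988 (not close) both reproduce. At N=195, .936 reproduces (.937) and .822 comes out at .792. None of these concerns the indirect path, for which the plan gives no figure.

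**2. Inputs.**
- From the documents: waves at 0, 4, 8 and 12 months; N=300 planned (309 evaluated); alpha .01; AAQ-II retest .80 at 3 months and .78 at one year; AAQ-II with depression r = -.71; QLS retest .78 to .84.
- Assumed: two-sided tests, and the correlations of functioning with symptoms and with the predictors. The documents do not give these correlations, so they are varied.

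**3. Hand check.** Take a 4-month predictor X, 8-month mediator M and 12-month outcome Y. Each is autoregressive with wave-to-wave stability s = .80, every concurrent correlation is r = .3, and all lagged effects are zero.
- corr(X4, M8) = s·r = .24; corr(M8, Y12) = .24; corr(X4, Y12) = s²·r = .192.
- Path a = .24, SE = √[(1 - .0576)/298] = .0562, z = 4.27.
- Path b, given X4: (.24 - .192 × .24)/(1 - .0576) = .206. With R² = .077, SE = √[.923/(297 × .9424)] = .0574, z = 3.58.
- Chance that both exceed 2.576: about Φ(1.69) × Φ(1.01) = .95 × .84 = .80.
- Sobel: ab = .0494, SE = √(.24² × .0574² + .206² × .0562²) = .0180, z = 2.74, chance about Φ(.17) = .57.

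The true lagged effect is zero, yet the expected result is significant.

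**4. Simulation of the plan's model.** One predictor, one mediator, direct path kept, N=300, stability .80, lagged effects zero, 2,000 replicates, observed scores standing in for latent factors. Entries are the share of studies with a significant indirect path. 'Joint' means both paths at p < .01. 'Trait' means stable correlated traits plus independent noise at each wave.

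| Correlations | AR(1), Sobel | AR(1), joint | Trait, Sobel | Trait, joint |
|---|---|---|---|---|
| all .2 | 5.7% | 26% | 20% | 53% |
| all .3 | 55% | 81% | 84% | 93% |
| .71/.5/.6 | 100% | 100% | 100% | 100% |

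A separate autoregressive run that also took lower stability (near .7) gives about 2-5% (Sobel) or 14-26% (joint) at .2, 25-53% or 58-80% at .3, and over 95% at .5. Its upper ends match the .80 column within simulation error. With uncorrelated scales the rate is about 0%, and at .1 (AR(1)) about 1%. At N=195 the joint rates are 10% and 50% (AR(1)) or 26% and 71% (trait) at .2 and .3.

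**5. The full layout.** Four 4-month and three baseline predictors make 7; with 2 mediators there are 7 × 2 = 14 indirect paths. Joint test, r from .2 to .5, 1,000 replicates: a single path is falsely significant in 2-24% (AR(1)) or 2-7% (trait), and at least one of 14 in 16-88% or 12-32%.

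**6. Adding earlier levels** (one predictor, one mediator, joint test).
- Immediately preceding wave only: 0.0-0.1% (AR(1)), but 0.4% to 66% (trait), rising with the correlations.
- All earlier waves, trait data: 0.2% to 11%.
- Which case applies: stability .80 per 3 months in an AR(1) process implies .80⁴ = .41 at one year, whereas the AAQ-II figure is .78. That looks trait-like, so one lag is not enough.

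**7. Where adjustment would do harm.** Deployment and pre-deployment stress precede baseline. If they truly act through symptoms, baseline and 4-month symptoms already carry that effect. Simulating true full mediation (assumed parameters), conditioning 8-month symptoms on earlier symptoms cuts detection from 75-100% to about 1%.

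**The case against.** **Phase I is over.** Data collection ended in June 2014 and the data moved to the repository in November 2021. This stands. The point cannot change conduct and bears only on analysis, reporting and re-use.

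**The plan promises less than a reader might infer.** One might read the rationale as a claim to remove stable response style. It speaks only of bias at a particular assessment, and time separation does address that. The criticism is that the layout leaves stable differences untouched, not that the authors said otherwise.

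**Aim 4 does not rest on this test alone.** A reader might infer that Hypotheses 4a to 4c all depend on it. They do not: Aim 4 is pursued first by comparing models, Hypothesis 4a is itself about comparative fit, and the over-time test is additional. The cross-lag panel can also give an adjusted check of the link from symptoms to functioning. It does not test the indirect path.

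**The largest rates come from a simplified model.** This stands. Per-path rates fall to 2-24% when all predictors and mediators enter together, and the -.71 is one pair of scales only.

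**Blanket adjustment would erase real mediation.** This also stands for exposures before baseline, and the fix is limited accordingly.

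**Conclusion.** The omission is in the text and is specific to the over-time mediation model. As written, a significant indirect path there cannot be taken as evidence of mediation over time, because stable correlated scales can produce one without any lagged effect.

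How often depends on correlations that the documents do not supply: about 1% at .1 (autoregressive data), a material excess by .3, and near certainty at .5 in the one-predictor case. The full-layout rates are the better guide to the planned analysis. Everything rests on observed-score regressions in place of the latent-variable model.

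It would be tempting to conclude that Phase I mediation findings are spurious. The documents report no such results and do not support that.

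**What to change.** In the over-time Aim 4 model:

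1. Adjust 12-month functioning for functioning at all earlier waves.
2. For the 4-month predictors, adjust 8-month PTSD-Depression and AUD symptoms for their baseline and 4-month values.
3. For pre-deployment stress, deployment stress and baseline neurocognition, do not test the path to 8-month symptoms conditional on earlier symptoms. Let them predict baseline symptoms, and carry the indirect effect along the chain from baseline to 8-month symptoms.
4. Add a random intercept as a sensitivity analysis, because the retest figures look trait-like.
5. Re-estimate any existing over-time mediation result that lacks prior levels, or label it unadjusted, including when repository data are re-used.

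No new data are needed. The Phase I instrument table ticks WHODAS II (the "36 item self-report version assessing functional disability across 7 domains"), QLS, PCL-5, BDI-II and DDQ-R at every wave.

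The costs are smaller indirect effects, some no longer reaching .01, and prior-wave factors limited to indicators collected at 4 and 8 months: CAPS, SCID, RAPI and IFI are ticked only at baseline and 12 months. Separately, Brief COPE and the DRRI have no 4/8-month tick, so the source of 4-month active coping and social support needs to be stated.
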